9.2 INFLUENZA SYMPTOM SCORE CARD OF FLU010 - BE-80-1800488

Group	Subject	Screening number:
-------	---------	-------------------

^a Fill in the SSC twice daily, at approximately 12h intervals (AM and PM) starting on Day1.
^b Score the severity of the symptoms with 0: absent, 1: mild, 2: moderate or 3: severe – each field should be filled out.
^c For the current score of a symptom, fill in the worse severity during the period between 2 SSC's.

	Day1		Day2		Day3		Day4		Day5		Day6		Day7		Day8		Day9		Day10		Day11
	AM	PM	AM	PM																	
Time point of collection (HH:MM)																					
Medication taken during the last 12h?	Y/N	Y/N	Y/N	Y/N																	
Feel well enough to go to work today?	Y/N	Y/N	Y/N	Y/N																	
Respiratory tract (upper + lower)																					
Blocked nose																					
Runny nose																					
Sneezing frequency																					
Sinus pressure/pain or facial pain																					
Sore throat																					
Difficulty swallowing																					
Teary/ watery eyes																					

Statistical Analysis Plan

FLU010

Final analysis

Final 3.0 of 15JUN2020

	Statistical Analysis Plan													
FLU010	Final analysis										Final 3.0 of 15JUN2020			

Interviewer initials															
Investigator initials															
Lymphadenopathy?															
Moderate/ severe sign/symptom of lower respiratory tract involvement?	Y/N														

	Statistical Analysis Plan	
	Final analysis	Final 3.0 of 15JUN2020

9.3 TOXICITY GRADES

Toxicity Grading Scale for Healthy Adult and Adolescent Volunteers Enrolled in Preventive Vaccine Clinical Trials, CBER, September 2007

PARAMETER	Unit	GRADE 1	GRADE 2	GRADE 3	GRADE 4
Amylase [pancreatic]		1.1-1.5 *ULN	>1.5-2.0 *ULN	>2.0-5.0 *ULN	>5.0 *ULN
Alanine amino transferase		1.1-2.5 *ULN	>2.5-5.0 *ULN	>5.0-10.0 *ULN	>10.0 *ULN
Albumin	g/L	31-28	<28-25	<25	-
	g/dL	3.1-2.8	<2.8-2.5	<2.5	-
Alkaline phosphatase		1.1-2.0 *ULN	>2.0-3.0 *ULN	>3.0-10.0 *ULN	>10.0 *ULN
Aspartate amino transferase		1.1-2.5 *ULN	>2.5-5.0 *ULN	>5.0-10.0 *ULN	>10.0 *ULN
Bilirubin [total]		1.1-1.5 *ULN	>1.5-2.0 *ULN	>2.0-3.0 *ULN	>3.0 *ULN
Blood urea nitrogen	mmol/L	8.2-9.3	>9.3-11.1	>11.1	-
	mg/dL	23-26	>26-31	>31	-
Calcium low	mmol/L	2.10-2.00	<2.00-1.87	<1.87-1.75	<1.75
	mg/dL	8.4-8.0	<8.0-7.5	<7.5-7.0	<7.0
Calcium high	mmol/L	2.62-2.74	>2.74-2.87	>2.87-2.99	>2.99
	mg/dL	10.5-11.0	>11.0-11.5	>11.5-12.0	>12.0
Cholesterol	mmol/L	5.20-5.43	>5.43-5.82	>5.82	-
	mg/dL	201-210	>210-225	>225	-
Creatinine	mmol/L	0.133-0.150	>0.150-0.177	>0.177-0.221	>0.221
	mg/dL	1.5-1.7	>1.7-2.0	>2.0-2.5	>2.5
Creatine [phospho] kinase		1.25-1.50 *ULN	>1.50-3.00 *ULN	>3.00-10.00 *ULN	>10.00 *ULN

	Statistical Analysis Plan				
	FLU010	Final analysis			Final 3.0 of 15JUN2020

Glucose fasting low	mmol/L	3.83-3.61	<3.61-3.05	<3.05-2.50	<2.50
	mg/dL	69-65	<65-55	<55-45	<45
Glucose fasting high	mmol/L	5.55-6.11	>6.11-6.94	>6.94	-
	mg/dL	100-110	>110-125	>125	-
Glucose non-fasting low	mmol/L	3.83-3.61	<3.61-3.05	<3.05-2.50	<2.50
	mg/dL	69-65	<65-55	<55-45	<45
Glucose non-fasting high	mmol/L	6.11-6.94	>6.94-11.10	>11.10	-
	mg/dL	110-125	>125-200	>200	-
Lipase		1.1-1.5 *ULN	>1.5-2.0 *ULN	>2.0-5.0 *ULN	>5.0 *ULN
Magnesium	mmol/L	0.62-0.53	<0.53-0.45	<0.45-0.37	<0.37
	mg/dL	1.5-1.3	<1.3-1.1	<1.1-0.9	<0.9
Phosphate	mmol/L	0.81-0.74	<0.74-0.65	<0.65-0.52	<0.52
	mg/dL	2.5-2.3	<2.3-2.0	<2.0-1.6	<1.6
Potassium low	mmol/L	3.6-3.5	<3.5-3.3	<3.3-3.1	<3.1
	mEq/L	3.6-3.5	<3.5-3.3	<3.3-3.1	<3.1
Potassium high	mmol/L	5.1-5.2	>5.2-5.4	>5.4-5.6	>5.6
	mEq/L	5.1-5.2	>5.2-5.4	>5.4-5.6	>5.6
Protein	g/L	60-55	<55-50	<50	-
	g/dL	6.0-5.5	<5.5-5.0	<5.0	-
Sodium low	mmol/L	134-132	<132-130	<130-125	<125
	mEq/L	134-132	<132-130	<130-125	<125

	Statistical Analysis Plan				
	FLU010	Final analysis			Final 3.0 of 15JUN2020

Sodium high	mmol/L	144-145	>145-147	>147-150	>150
	mEq/L	144-145	>145-147	>147-150	>150
Prothrombin time		1.00-1.10	>1.10-1.20	>1.20-1.25	>1.25
Partial thromboplastin time		1.0-1.2	>1.2-1.4	>1.4-1.5	>1.5
Fibrinogen low	μmol/L	5.88-4.41	<4.41-3.68	<3.68-2.94	<2.94
	mg/dL	200-150	<150-125	<125-100	<100
Fibrinogen high	μmol/L	11.76-14.70	>14.70-17.65	>17.65	-
	mg/dL	400-500	>500-600	>600	-
Eosinophils	giga/L	0.65-1.50	>1.50-5.00	>5.00	-
	counts/mm ³	650-1500	>1500-5000	>5000	-
Hemoglobin [female] ^[1]	mmol/L	7.27-6.67	<6.67-5.76	<5.76-4.85	<4.85
	g/dL	12.0-11.0	<11.0-9.5	<9.5-8.0	<8.0
Hemoglobin [male] ^[1]	mmol/L	8.18-7.58	<7.58-6.36	<6.36-5.15	<5.15
	g/dL	13.5-12.5	<12.5-10.5	<10.5-8.5	<8.5
Hemoglobin, as decrease from baseline ^[2]	mmol/L	<0.00 to -0.91	<-0.91 to -1.21	<-1.21 to -3.03	<-3.03
	g/dL	<0.0 to -1.5	<-1.5 to -2.0	<-2.0 to -5.0	<-5.0
Lymphocytes [absolute count]	giga/L	1.00-0.75	<0.75-0.50	<0.50-0.25	<0.25
	counts/mm ³	1000-750	<750-500	<500-250	<250
Neutrophils [absolute count]	giga/L	2.0-1.5	<1.5-1.0	<1.0-0.5	<0.5
	counts/mm ³	2000-1500	<1500-1000	<1000-500	<500
Platelets	giga/L	140-125	<125-100	<100-25	<25

	Statistical Analysis Plan	
FLU010	Final analysis	Final 3.0 of 15JUN2020

	counts/mm ³	140000-125000	<125000-100000	<100000-25000	<25000
White blood cells low	giga/L	3.5-2.5	<2.5-1.5	<1.5-1.0	<1.0
	counts/mm ³	3500-2500	<2500-1500	<1500-1000	<1000
White blood cells high	giga/L	10.8-15.0	>15.0-20.0	>20.0-25.0	>25.0
	counts/mm ³	10800-15000	>15000-20000	>20000-25000	>25000

^[1] Preferred, defined on actual values. ^[2] Alternative; decrease implies negative changes. Only one should be computed, either ^[1] or ^[2].

 FLU010	Statistical Analysis Plan										
	Final analysis								Final 3.0 of 15JUN2020		

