9.1.3 Safety Data

Safety parameters will be tabulated and analysed descriptively.

Adverse Events

The original terms used in the eSource documents by Investigators to identify AEs will be fully described and coded according to the Medical Dictionary for Regulatory Activities (MedDRA).

The reported AEs will be allocated to phases based on their start date. All AEs will be listed. All AEs with onset after Day 1 of vaccination will be summarized by treatment group. Summaries, listings, and narratives may be provided, as appropriate. Summaries will include at a minimum SAEs, and for both solicited and unsolicited AEs, the severe (grade 3+ events), related AEs, and AEs following challenge.

Clinical Laboratory Tests

Each continuous biochemistry and haematology laboratory test will be evaluated by means of descriptive statistics (i.e., number of participants, mean, SD, median, minimum, and maximum) on the actual values, at each assessment time point and by vaccination group.

Relative changes in clinical laboratory test values compared to values at baseline will be evaluated according to the appended toxicity scale or in accordance with the normal ranges of the clinical laboratory (below, within, or above normal range) for parameters for which no toxicity grades are defined.

A listing of participants with any clinical laboratory test result outside the reference ranges will be provided.

Vital Signs

Pulse rate, temperature, SBP, and DBP will be evaluated by means of descriptive statistics (actual values and changes from Day 1 to Day 2 of the vaccine phase and from Day 1 of the challenge phase and frequency tabulations at each assessment time point and by vaccination group).

Pulse oximetry will be measured during the entire challenge phase.

The percentage of participants with values beyond clinically important limits (as defined in the Toxicity Tables) will be summarized.

Electrocardiogram

ECG variables will be evaluated by means of descriptive analysis by the Investigator at each assessment time point.

The percentage of participants with ECG abnormalities will be summarized.

The ECG variables that will be analysed by electronic capture from the ECG include heart rate, PR interval, QRS interval, QT interval.

Physical Examination

Abnormal findings in physical examination will be listed.

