Potassium – Hypokalemia mEq/L	3.5 – 3.6	3.3 – 3.4	3.1 – 3.2	< 3.1
Glucose – Hypoglycemia mg/dL	65 – 69	55 – 64	45 – 54	< 45
Glucose – Hyperglycemia				
Fasting – mg/dL	100 – 110	111 – 125	>125	Insulin requirements or hyperosmolar coma
Random – mg/dL	110 – 125	126 – 200	>200	
Blood Urea Nitrogen BUN mg/dL	23 – 26	27 – 31	> 31	Requires dialysis
Creatinine – mg/dL	1.5 – 1.7	1.8 – 2.0	2.1 – 2.5	> 2.5 or requires dialysis
Calcium – hypocalcemia mg/dL	8.0 – 8.4	7.5 – 7.9	7.0 – 7.4	< 7.0
Calcium – hypercalcemia mg/dL	10.5 – 11.0	11.1 – 11.5	11.6 – 12.0	> 12.0
Magnesium – hypomagnesemia mg/dL	1.3 – 1.5	1.1 – 1.2	0.9 – 1.0	< 0.9
Phosphorous – hypophosphatemia mg/dL	2.3 – 2.5	2.0 – 2.2	1.6 – 1.9	< 1.6
CPK – mg/dL	1.25 – 1.5 x ULN***	1.6 – 3.0 x ULN	3.1 – 10 x ULN	> 10 x ULN
Albumin – Hypoalbuminemia g/dL	2.8 – 3.1	2.5 – 2.7	< 2.5	--
Total Protein – Hypoproteinemia g/dL	5.5 – 6.0	5.0 – 5.4	< 5.0	--
Alkaline phosphate – increase by factor	1.1 – 2.0 x ULN	2.1 – 3.0 x ULN	□ 3.1 – 10 x ULN	> 10 x ULN
Liver Function Tests –ALT, AST increase by factor	1.1 – 2.5 x ULN	2.6 – 5.0 x ULN	5.1 – 10 x ULN	> 10 x ULN
Bilirubin – when accompanied by any increase in Liver Function Test increase by factor	1.1 – 1.25 x ULN	1.26 – 1.5 x ULN	1.51 – 1.75 x ULN	> 1.75 x ULN
Bilirubin – when Liver Function Test is normal; increase by factor	1.1 – 1.5 x ULN	1.6 – 2.0 x ULN	2.0 – 3.0 x ULN	> 3.0 x ULN
Cholesterol	201 – 210	211 – 225	> 226	---
Pancreatic enzymes – amylase, lipase	1.1 – 1.5 x ULN	1.6 – 2.0 x ULN	2.1 – 5.0 x ULN	> 5.0 x ULN

* The laboratory values provided in the tables serve as guidelines and are dependent upon institutional normal parameters. Institutional normal reference ranges should be provided to demonstrate that they are appropriate.

** The clinical signs or symptoms associated with laboratory abnormalities might result in characterization of the laboratory abnormalities as Potentially Life Threatening (Grade 4). For example, a low sodium value that falls within a grade 3 parameter (125-129 mEq/L) should be recorded as a grade 4 hyponatremia event if the participant had a new seizure associated with the low sodium value.

*** ULN" is the upper limit of the normal range.

Hematology *	Mild (Grade 1)	Moderate (Grade 2)	Severe (Grade 3)	Potentially Life Threatening (Grade 4)
Hemoglobin (Female) - gm/dL	11.0 – 12.0	9.5 – 10.9	8.0 – 9.4	< 8.0
Hemoglobin (Female) change from baseline value - gm/dL	Any decrease – 1.5	1.6 – 2.0	2.1 – 5.0	> 5.0

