3.2.2 Derivation rules

Toxicity grades will be computed according to the Centre for Biologics Evaluation and Research (CBER) toxicity grading list. The implementation of these toxicity grades for analysis is presented in appendix 9.2. Only the parameters described in appendix 9.2 will be computed, according to the declared limits for each grade.

For parameters for which no toxicity grades are defined, the following abnormality categories will be defined:

- Low: value < lower limit of normal range
- Normal: lower limit of normal range \leq value \leq upper limit of normal range
- High: value > upper limit of normal range

Note:

- Classification will be done in standardised units, using non imputed values and limits.
- For the worst-case analysis visit, as defined in section 5.2.5, an additional category low + high is defined in case there are both low and high values within the same phase.

	Statistical Analysis Plan	
FLU010	Final analysis	Final 3.0 of 15JUN2020

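### SAP 9.3 grades bilirubin only on the protocol's normal-liver-test scale, so with raised ALT or AST the bilirubin grade is one or two too low between 1.26 and 3.0 x ULN

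*SAP*

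**What the plan says.** **Protocol.** Section 9.1.3 (Clinical Laboratory Tests) states that laboratory changes from baseline "will be evaluated according to the appended toxicity scale", or by the laboratory's normal ranges where no toxicity grade exists. The scale is Appendix 2, part B. It has two bilirubin rows:

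- "Bilirubin – when accompanied by any increase in Liver Function Test increase by factor"
- "Bilirubin – when Liver Function Test is normal; increase by factor"

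The same table shows which tests it means by liver function tests: "Liver Function Tests –ALT, AST increase by factor". Alkaline phosphatase has a separate row without that label.

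**SAP.** Section 3.2.2 grades laboratory values on the CBER list and adds: "Only the parameters described in appendix 9.2 will be computed, according to the declared limits for each grade". The appendix it cites, 9.2, is the influenza symptom score card; the grading table is in 9.3. That table has one bilirubin row, "Bilirubin [total" (total bilirubin), with no condition on any other test. SAP 6.1, on departures from the protocol before database lock, is marked not applicable. The SAP change log in 6.3 does not mention bilirubin.

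**The concern.** The SAP presents its table as an implementation of the scale that the protocol appends, but half of the bilirubin grading is missing. The missing half is the conditional one, which makes a given bilirubin value count for more when a transaminase is raised as well. The SAP's toxicity tables are otherwise built parameter by parameter, so this condition is the only place where the grading takes account of a joint rise.

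The grades feed three outputs: the overview row for treatment-emergent Grade 3 or higher laboratory toxicity (SAP 3.1.3), the cross-tabulations against baseline, and the worst-case visit (SAP 3.2.3, Table 14.3.2.3). Any error runs in one direction, towards milder bilirubin grades.

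The omission does not look deliberate. Where the source scale offers alternatives elsewhere, SAP 9.3 shows them: glucose is split by fasting state, haemoglobin by sex, and a footnote says which of two haemoglobin definitions is preferred. Bilirubin has no such note.

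**Working it through.** The plan gives no figure to reproduce. The check sets the printed limits side by side, with x = bilirubin / ULN.

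| Grade | Protocol, liver test increased | Protocol, liver tests normal | SAP 9.3, unconditional |
|---|---|---|---|
| 1 | 1.1-1.25 | 1.1-1.5 | 1.1-1.5 |
| 2 | 1.26-1.5 | 1.6-2.0 | >1.5-2.0 |
| 3 | 1.51-1.75 | 2.0-3.0 | >2.0-3.0 |
| 4 | >1.75 | >3.0 | >3.0 |

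**Step 1: which protocol scale is the SAP row?** The protocol's normal-liver-test row leaves 1.5 to 1.6 unassigned and puts 2.0 in two grades. If these edges are closed as the SAP closes them (>1.5, >2.0), the SAP row and that protocol row agree at every 0.01 step from 1.00 to 4.00 x ULN. The SAP row is therefore the normal-liver-test scale.

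**Step 2: grade gap when ALT or AST is increased.** Gap = protocol grade (liver test increased) minus SAP grade.

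| Bilirubin (x ULN) | Protocol grade | SAP grade | Gap |
|---|---|---|---|
| 1.10-1.25 | 1 | 1 | 0 |
| 1.26-1.50 | 2 | 1 | 1 |
| 1.51-1.75 | 3 | 2 | 1 |
| 1.76-2.00 | 4 | 2 | 2 |
| 2.01-3.00 | 4 | 3 | 1 |
| above 3.00 | 4 | 4 | 0 |

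Single values: 1.3 x ULN is Grade 2 against 1; 1.6 is 3 against 2; 1.8 is 4 against 2; 2.5 is 4 against 3.

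**Step 3: effect on the Grade 3 or higher row.** The protocol reaches Grade 3 in the band "1.51 – 1.75 x ULN" and Grade 4 above it. The SAP reaches Grade 3 only above 2.0. With ALT or AST increased, bilirubin above 1.5 and up to 2.0 x ULN is thus Grade 3 or 4 by the protocol and Grade 2 by the SAP. Above 2.0 the value is in the row under either scale, although up to 3.0 its grade is still one too low.

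**Step 4: can the stricter scale be applied?** Yes. Bilirubin, ALT and AST are in one biochemistry panel (Protocol 7.2.3, SAP 3.2.1). It is scheduled at Screening 2, before challenge (Day -2 or -1), and on challenge Days 2 and 8.

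**The case against.** The case for leaving this as a minor item has substance.

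- **Little is hidden.** All laboratory data are listed for any participant with a post-baseline abnormality (Listing 16.2.8.1). Bilirubin, ALT and AST are each summarised, and the investigator reviews every result. This stands.
- **Reach is probably small.** Participants are healthy adults screened for clinically significant laboratory abnormalities, with few biochemistry time points after vaccination. This is plausible, but the documents do not allow a count.
- **Appendix 2 calls its limits guidelines that depend on institutional normal parameters.** That could justify different limits. It does not explain leaving out a conditional scale without saying so.

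A reader might also infer more than the documents support:

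- *That affected values disappear from the shift tables.* They do not. SAP 3.2.3 cross-tabulates all grades, so the value stays in the table at a lower grade.
- *That the participant is lost from the Grade 3 or higher count.* Not necessarily. ALT and AST keep their own rows, and either above 5.0 x ULN is Grade 3 or higher on its own. What is lost is the bilirubin contribution, and the participant only if no other parameter reaches Grade 3.
- *That the report could contradict a challenge halt.* Nothing links SAP-computed grades to Protocol 8.3. The laboratory criterion there also requires relatedness to the challenge agent and concern on the part of the investigator or medical monitor. Nor is it settled which scale the site would use: Protocol 7.2.2 scores AEs by Appendix 2, while 10.2 rates them by CTCAE.
- *That raised alkaline phosphatase should also trigger the stricter scale.* Appendix 2 gives the liver function test label to ALT and AST only.

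**Conclusion.** The discrepancy is real and undeclared. Followed as written, the SAP assigns a lower bilirubin grade than the protocol's own scale whenever ALT or AST is increased and bilirubin is between 1.26 and 3.0 x ULN. The shortfall is two grades only above 1.75 and up to 2.0 x ULN; elsewhere in that range it is one grade. The Grade 3 or higher row loses bilirubin's contribution only above 1.5 and up to 2.0 x ULN.

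This rests on two readings: that liver function tests means ALT and AST, as Appendix 2 labels them, and that the small gaps between printed bands are closed as the SAP closes them. The protocol does not define an increase. Above ULN and at least 1.1 x ULN (where Grade 1 starts for ALT and AST) are both possible, and they differ only for transaminases between those two values.

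Only descriptive safety tables are affected; the primary endpoint is untouched. The correction is still worth making because it is cheap and the grading errs only towards milder bilirubin grades.

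**What to change.** 1. In SAP 9.3, replace the single bilirubin row with the two Appendix 2 rows. Apply 1.1-1.25 / 1.26-1.5 / 1.51-1.75 / >1.75 x ULN when ALT or AST from the same sample is increased, and the present row otherwise. Do not use alkaline phosphatase as a trigger.
2. State the cut-off for increased, for example above ULN, and close the band edges explicitly (>1.25, >1.5).
3. Grade each baseline sample by the same rule, using its own ALT and AST, because treatment-emergent status is judged against baseline.
4. In SAP 3.2.2, change both references to appendix 9.2 to 9.3.
5. Record the change in SAP 6.3. If the sponsor instead wants one scale for all participants, SAP section 6 should declare that departure from Protocol 9.1.3 and give the reason.

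The cost is one extra table row, one programming condition, and a rerun of any affected laboratory toxicity outputs already produced. No new data are needed.

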9.4 SCHEDULE OF ASSESSMENTS

9.4.1 Period 1- Screening and Vaccination Schedule

Period 1	Screening 1	Screening 2	Baseline Vaccination	Out-patient Clinic Visit	Phone ^m	Out-patient Clinic Visit	Out-patient Clinic Visit	Phone ^m	Unscheduled visit ^l	See Challenge Day -2	Phone
	Days -42 to -2	Day -21 to -1	Day 1	Day 2	Day 4	Day 8 ±1 (Week 1 Visit)	Day 28±3	Day 56±3			Month 6 (180 ±14 days) ⁿ
Informed Consent	x ^a	x ^a									
Inclusion/Exclusion	x ^b	x ^b									
Randomization			x								
Medical History/Demography		x									
Physical Examination		x ^c				x	x		x		
Vital Signs		x				x	x		x		
Supine 12-lead ECG		x									
Haematology		x							x		
Biochemistry ^d		x							x		
Microneutralization (MNT) ^a	x	x ^a									
Urinalysis		x							x		
HIV,, Hep C, HBsAg		x									
Urine Drug Screen		x	x						x		
Alcohol breath test		x	x						x		
Serum/Urine Pregnancy ^e		x ^e	x						x		

 FLU010	Statistical Analysis Plan										
	Final analysis								Final 3.0 of 15JUN2020		

Blood sample for cellular immunogenicity assays PBMCs ^f , and Serum			x ^g			x	x				
Transcriptomics - whole blood collection (PAXgene® RNA)			x ^g	x ^h		x	x				
Vaccination			x								
Dispense/Remind/Collect Diary Cards			x ^j		x ⁱ	x ^k					
AEs/Con-meds	x	x	x	x	x	x	x	x	x	x ⁿ	

^a If MNT was completed for another study within 6 weeks prior to vaccination then this test does not need to be completed for this study. Informed Consent Form (ICF) signature will be performed at Screening visit prior any study procedures take place. Also, to ensure a sufficient number of participants are vaccinated in a given group, MNT may be performed at Screening 2 at the same time as Screening 2 assessments

^b Some inclusion/exclusion criteria will be checked at Screening 1 visit to ensure participants are potentially eligible prior to MNT test

^c Physical examination at screening will include height and weight measurements

^d Biochemistry test includes creatinine, glucose, aspartate aminotransferase (AST), alanine aminotransferase (ALT), alkaline phosphatase (ALP), gamma glutamylaminotransferase (GGT), C-reactive protein (CRP), and bilirubin

^e Serum sample will be used for pregnancy test at screening and urine pregnancy test will be used in subsequent visits

^f PBMCs to be sent to Viroclinics for processing

^g PBMC, Serum and Transcriptomics samples at Day 1 are to be collected pre-vaccination

^h Transcriptomics sample on Day 2 is to be collected 24 hours (± 3 hours) post-vaccination

ⁱ Phone call to participants to remind them to complete Diary Card

^j Distribute Diary Cards to participants

^k Collect completed Diary Cards from participants (up to Day 8)

^l Assessments during Unscheduled Visits are performed at the discretion of the Investigator

^m During phone visits, AEs and ILIs will be collected and participants will be reminded about their potential next visits including the challenge period start

ⁿ Month 6 visit post-vaccination day (180 days ±14) will be performed for all vaccinated participants if it is later than Day 28 post-Challenge

 FLU010	Statistical Analysis Plan														
	Final analysis													Final 3.0 of 15JUN2020	

9.4.2 Period 2 – Challenge Schedule

Period 2	In-Clinic Confinement													Unsched Visit ^c	Out-patient
	Day -2	Day -1	Day 1	Day 2	Day 3	Day 4	Day 5	Day 6	Day 7	Day 8	Day 9	Day 10	Day 11		
Screening/Administrative/Other Assessments															
Eligibility Criteria	x														
Medical and Medication History Review	x														
Ambulatory Visit															x
Admission to study unit / discharge	Admission ^a Confinement													Discharge	
Full Days Residence		x	x	x	x	x	x	x	x	x	x	x	x		
Safety Assessments															
Physical Exam	x													x	x
Symptom-Directed Physical Examination		x	x	x	x	x	x	x	x	x	x	x	x		x
Vital Signs	x	x	x	x	x	x	x	x	x	x	x	x	x	x	x
Spirometry		x											x		x
Peak Flow		x	x	x	x	x	x	x	x	x	x	x	x		x
Supine 12-lead ECG ^g		x				x								x	x
Pulse oximetry		x	x	x	x	x	x	x	x	x	x	x	x		
Drug / Alcohol Screen	x													x	
Urine Pregnancy Test	x													x	x

 FLU010	Statistical Analysis Plan															
	Final analysis													Final 3.0 of 15JUN2020		

Biochemistry ^e	x ^a			x						x					x		
Haematology	x ^a			x						x					x		
Symptom Score (Questionnaire) – b.i.d.			x	x	x	x	x	x	x	x	x	x	x	x ^d			
Concomitant therapy - AEs/ SAEs	x	x	x-----x													x	x
Study Agent Administration / Pharmacokinetic and Immunogenicity Assessments																	
Viral Inoculation			x														
NP swabs samples for qualitative PCR testing - multiple viruses - (CPU Antwerp) ^b	x												x				
NP swabs sample for viral load by qPCR (culture done if positive) – b.i.d. (after challenge)				x	x	x	x	x	x	x	x	x	x				
Tissue Collection for Mucus weights ^h			x	x	x	x	x	x	x	x	x	x	x	x			
Blood sample for humoral immunogenicity (MNT) and Hemagglutination Inhibition (HI) assays ⁱ	x ^a																x
Blood sample for cellular immunogenicity assays PBMCs ^j	x ^a																x
Transcriptomics - whole blood collection (PAXgene® RNA)	x ^k	x ^k		x				x			x						x

^a Admission to clinic is possible on Day -1, in which case Day -2 assessments may be performed on Day -1. Pre-challenge assessments may be performed on Day -2 or Day -1.

^b Multiplex PCR tests are to be performed to determine whether participants are incubating other viruses at the time of inoculation. Participants with positive results should not enter the challenge group and could be offered to be part of one of the subsequent groups if their infection is cleared.

^c Assessments during Unscheduled Visits will be performed at the discretion of the Investigator

